There are three primary Veteran-reported trial outcomes which will be measured at 5- and 12-months post enrollment: 1) confidence in symptom self-management, 2) implementation of symptom self-management, and 3) symptom burden and PC-QOL. Self-efficacy in patient-physician interactions will also be assessed at baseline, 5-months and 12-months. Participants in the trial will be randomized by computer by VA Ann Arbor Healthcare System (VAAHS) study staff. We hypothesize better outcomes in the intervention arm relative to enhanced usual care. The impact of the intervention on two secondary psychosocial outcomes, overall subjective health and perceptions of cancer control, will be assessed only at the 12-month time point, when we believe the intervention is most likely to have had its impact on these outcomes. The trial will be conducted in four VA sites (Ann Arbor, Cleveland, Pittsburgh, and St. Louis) with a large and racial/ethnically diverse population of PC survivors between 1-10 years post-treatment. The intervention is based on a conceptual framework that describes how self-management contributes to positive outcomes for cancer patients and survivors; we also will utilize theoretical constructs from patient empowerment and cognitive behavioral therapy (CBT) to inform the content of our intervention. We will compare the quality of health care received in intervention and control subjects using guidelines for prostate cancer survivorship care developed by the Michigan Cancer Consortium as a benchmark. Finally, we will prepare for implementation of the intervention on a broader scale through a formative evaluation. This design will allow us to understand how the intervention can best optimize the quality of life and quality of care for Veterans with PC, and will inform how to implement the program more broadly with our primary care partners.

- **Include a description of how anticipated risk will be minimized and include an analysis of risk vs. potential benefit.**

How anticipated risk will be minimized:

Veteran participants:

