At the end of the intervention delivery phase, the research team will conduct semi-structured interviews with up to 40 key stakeholders (up to 4 PCPs and 4 specialists at each site, plus interviews of stakeholders at the VISN and national level). Drs. [name] and [name] will arrange interviews with up to 4 PCPs at each site (with the support of the primary care service director) and 4 specialists providing PC survivorship care per site. Recruitment of these individuals will be done via email and phone, with introductory letters sent by [name] and the site PIs. Guided interviews will be conducted with these physicians in person or by telephone to assess perceptions of system factors contributing to positive intervention outcomes, and will be audiotaped with their verbal consent.

To identify participant factors influencing intervention effectiveness, we will re-contact participants in the intervention arm who achieved the best outcomes (i.e., had the highest reduction in symptom burden over the study period) and the worst outcomes (i.e., no change in symptom burden or increase in symptom burden). Starting in month 9 of year 3, we will contact 5 participants at each site in the best outcome group, and 5 participants per site in the worst outcome group (N=40 total), based on preliminary data analyses available at that time. We will conduct in-depth interviews with these participants by telephone to determine patient perceptions and factors associated with the intervention's effectiveness. Participants in these interviews will be limited to patients who agreed to this interview during the 12-month follow-up survey. We will initiate re-contact during month 9 of year 3, and continue into months 1-2 of year 4. Telephone interviews are expected to take 30-40 minutes and will be audiotaped with the participants' verbal consent.

- **Describe materials that will be used to recruit subjects, e.g., advertisements. Include materials as an appendix or separate attachment.**

Potential participants will be sent an introductory letter and a patient information sheet. The letter will describe the study and include either a toll-free or local number to call if the patient is not interested in participating or would like more information.

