5.4 Inclusion/Exclusion Criteria

- **Describe the criteria that determine who will be included in or excluded from the study.**

Veteran participants:

Participants will be selected from CDW who meet the following eligibility criteria:

- Veteran patient at one of the four study sites
- History of treatment for prostate cancer treated by surgery, radiation or androgen deprivation therapy between 1-10 years prior to identification
- Has phone number on file and ability to converse on the telephone in English
- No dementia or other significant mental impairment

A random sample of those identified will be asked to participate. Those who elect to participate, and who have a qualifying Brief Screener score (1 or higher on at least 1 symptom) will be randomized to the study. We estimate as many as 553 - 650 veterans will be randomized. All participants will be 40-80 years old at the time of identification, and all will be male as this is a study of prostate cancer; otherwise we expect the health status of these veterans to be varied.

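### Choosing interviewees by raw change in symptom burden makes the best- and worst-outcome groups differ by over 1 SD at baseline, so the process evaluation mixes response with starting severity and regression to the mean (minor; cheap to fix)

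*Combined protocol and SAP*

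**What the plan says.** Section 5.2 (Recruitment Methods, Process Evaluation) gives the aim and the source of interviewees: "To identify participant factors influencing intervention effectiveness, we will re-contact participants in the intervention arm". The best group are those who "achieved the best outcomes (i.e., had the highest reduction in symptom burden over the study period". The worst group are those with "the worst outcomes (i.e., no change in symptom burden or increase in symptom burden". Five men per site are taken for the best group and "5 participants per site in the worst outcome group (N=40 total), based on preliminary data analyses available at that time". The interviews are qualitative: "We will conduct in-depth interviews with these participants by telephone to determine patient perceptions and factors associated with the intervention's effectiveness". Only men who agreed to an interview at the 12-month survey can be chosen.

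The rule does not say which of the four EPIC domains defines symptom burden, which visit is compared with baseline, or how the five are picked when more than five men at a site show no gain. It mentions neither baseline adjustment nor the control arm.

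Two other places matter. Section 5.4 sets a low entry threshold: men "who have a qualifying Brief Screener score (1 or higher on at least 1 symptom) will be randomized to the study". Section 5.5 scores each EPIC domain from 0 to 100, lower being worse, and treats 70 or less as clinically meaningful burden.

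**The concern.** Raw change is negatively correlated with baseline whenever the same measure is taken twice with imperfect correlation. Men who score unusually badly at entry tend to score better later without any treatment, and men who score unusually well tend to score worse. Ranking on raw change therefore fills the best group with men who started badly and the worst group with men who started well. Because all interviewees come from one arm, the change that would have happened anyway is not subtracted.

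The interviews are meant to identify participant factors behind effectiveness, and the abstract places the process evaluation beside a recommendation on wider deployment. A factor that distinguishes the two groups could simply be a marker of severity at entry. The groups would also look like responders and non-responders if the intervention did nothing.

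**Working it through.** **Inputs from the documents.** Correlation 0.5, difference 0.33 SD, alpha 0.0125, 90% power, 394 participants, 550 enrolled, 15% attrition at each assessment, 397 completers (section 5.6). Five best and five worst per site (section 5.2). Four sites (section 5.1: "The trial will be conducted in four VA sites (Ann Arbor, Cleveland, Pittsburgh, and St. Louis").

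**Assumptions.** Equal SDs at baseline and follow-up, approximate normality, one symptom score, equal arms and sites, and every completer willing to be interviewed.

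**1. The plan's own figures.** ANCOVA sample size per group is 2(1 - r²)(z₁ + z₂)²/d² = 2 × 0.75 × (2.498 + 1.282)²/0.33² = 196.8, so 197 per group and 394 in total, as stated (two-sided alpha). 550 × 0.85² = 397, as stated. (5 + 5) × 4 = 40 interviews, as stated. 397/(2 × 4) is about 50 intervention completers per site.

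**2. Change against baseline.** Let D be follow-up minus baseline EPIC, so a positive D is a reduction in burden. In baseline SD units, SD(D) = √(2(1 - r)) = 1 at r = 0.5. The correlation of D with baseline is -√((1 - r)/2) = -0.50, so baseline explains 25% of the variance of D.

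**3. Baseline of the selected groups at r = 0.5.**
- Best: the top 5 of 50 average about 1.70 SD above the mean change, so their baseline averages -0.50 × 1.70 = -0.85 SD.
- Worst, drawn from D ≤ 0, no intervention effect: mean D is -0.80, so baseline averages +0.40 SD. Gap: 0.85 + 0.40 = 1.25 SD.
- Worst, drawn from D ≤ 0, uniform 0.33 SD effect: 37% of men have D ≤ 0. They lie on average 0.378/0.371 = 1.02 SD below the mean change, so baseline averages +0.51 SD. Gap: 1.36 SD.
- If the five lowest changes are taken instead, baseline averages +0.85 SD and the gap is 1.70 SD.

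A simulation of 20,000 replicates with the 0.33 SD effect gave the same values. About 83% of the best group began below the mean and 71% of the D ≤ 0 group above it.

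**4. Range over r** (0.33 SD effect, worst drawn from D ≤ 0; gaps computed before rounding).

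| r | Corr(D, baseline) | Best, SD | Worst, SD | Gap, SD | Share of change contrast due to baseline |
|---|---|---|---|---|---|
| 0.3 | -0.59 | -1.01 | +0.58 | 1.59 | 35% |
| 0.5 | -0.50 | -0.85 | +0.51 | 1.36 | 25% |
| 0.7 | -0.39 | -0.66 | +0.42 | 1.09 | 15% |
| 0.8 | -0.32 | -0.53 | +0.36 | 0.90 | 10% |

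**5. Share due to baseline at r = 0.5, no effect.** Expected change falls by 1 - r = 0.5 per SD of baseline. The baseline gap therefore yields 0.5 × 1.25 = 0.62 SD, out of a difference in change of 1.70 + 0.80 = 2.50 SD, or 25%.

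**6. After baseline adjustment.** Follow-up minus its prediction from baseline is uncorrelated with baseline in this model, so both groups average 0.00 SD at baseline. Chance stays: with no effect, the five highest residuals still average about 1.70 × √0.75 = 1.47 SD above prediction.

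**7. Bounded scale (illustration only).** With an assumed EPIC mean of 75 and SD of 20, cut off at 0 and 100, the baselines are -1.20 (best) and +0.57 (worst, D ≤ 0) under raw selection. With linear adjustment, taking the five highest and five lowest residuals, they are -0.57 and -0.14. Over assumed means of 50 to 85 the share due to baseline is 25% to 46%.

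**The case against.** The strongest reply is that this is purposive sampling for a small qualitative study. Extreme outcomes are a way to choose informants, not to estimate an effect. Men can still say which calls, newsletters or goals they used. Each man's baseline EPIC is recorded, so the team can weigh severity when reading the transcripts, and the randomised comparison and up to 40 stakeholder interviews can also inform deployment. All of this stands, and it keeps the point minor. It does not justify building a known baseline imbalance into a contrast meant to find factors behind effectiveness when the data to remove it are collected anyway.

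Two stronger readings are tempting and are not supported.
- A reader might infer from the size of the baseline gap that the contrast is mostly baseline severity. Under the plan's correlation baseline accounts for about a quarter of the difference in change, and it stays below half even under the assumed ceilings above.
- A reader might infer that the worst group consists of men with little room to improve. The low entry threshold, with no domain named, makes this possible: a man near 100 in a domain that never troubled him would count as no change. But the documents give no baseline EPIC distribution, every man must report at least one symptom, and the worst group also includes men who got worse. The frequency of such men cannot be derived.

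It is also fair to say that adjustment equalises baseline but does not remove chance variation, and that section 5.2 relies on whatever preliminary data exist in month 9 of year 3. How complete the control data will be then is not stated. However, interviewees must already have reached the 12-month survey, and controls randomised over the same period supply the same EPIC data.

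**Conclusion.** The concern holds as a minor design weakness. As written, the two interview groups would differ at baseline by about 1.2 to 1.4 SD at the plan's own correlation when the worst group is drawn from men with no gain, and the lower end of that range arises with no intervention effect. The size rests on equal SDs, roughly normal scores, a single score and about 50 willing completers per site. Fewer willing men would make the best group less extreme and narrow the gap.

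A reader might go further and conclude that the interviews can reveal nothing about the intervention, or that the trial result is compromised. Neither follows. The interviews can generate hypotheses. What they cannot do under this rule is separate response from starting severity and natural change. No Aim 1 or Aim 2 estimate, test or sample size depends on the selection.

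**What to change.** In section 5.2, Process Evaluation:
- Name the EPIC domain and the time point. For example, use 12 months and a domain where the man's baseline was 70 or below, such as his lowest-scoring one.
- Rank intervention-arm men by observed minus predicted follow-up EPIC given baseline. Fit the prediction in control-arm men with data at that time, choosing their domain by the same rule. If different men are ranked on different domains, put the residuals on a common SD scale, since section 5.6 gives meaningful differences of 4 to 10 points depending on domain.
- Take the five highest and five lowest per site among men who agreed to an interview.
- State that the findings are exploratory.

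The cost is one regression on data already collected and a few sentences of protocol text, with no added interviews. There are three downsides: men with no domain at or below 70 could not be interviewed, a linear adjustment leaves some baseline difference if the ceiling is strong, and chance variation in individual change remains.

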5.3 Informed Consent Procedures

- **Indicate if informed consent will be obtained and/or if you are requesting a waiver of informed consent or waiver of documentation of informed consent. If the research involves multiple phases, specify for which phases of the research the waiver(s) is being requested and/or the informed consent will be sought.**

Describe who will be obtaining informed consent, if applicable, and any circumstances that may need to be addressed (e.g. subjects with impaired decision making ability and the use of a legally authorized representative, etc.)

We have obtained a waiver of documentation of informed consent and HIPAA authorization for the entirety of the study. Study staff will obtain verbal informed consent during the initial screening call (see patient recruitment script). Generally, the local coordinator will be responsible for recruitment of patients from her own site; however, we plan to add an additional coordinator at the coordinating center (VAAHS) who will be responsible for assisting with patient

recruitment at all three sites. Also, coordinators from all three sites may assist with recruitment at other sites in cases when a coordinator position is unfilled or due to extended leave.

- **If applicable, indicate how local site study personnel will be trained regarding human subjects protections requirements and how to obtain and document informed consent.**

Study staff sign a pledge of confidentiality and understand that breach of confidentiality is grounds for dismissal. Study staff are required to complete annual training on privacy and HIPPA, as well as biannual training on human subjects protection. We have obtained a waiver of documentation of informed consent and HIPAA authorization for the entirety of the study.

5.4 Inclusion/Exclusion Criteria

- **Describe the criteria that determine who will be included in or excluded from the study.**

Veteran participants:

Participants will be selected from CDW who meet the following eligibility criteria:

- Veteran patient at one of the four study sites
- History of treatment for prostate cancer treated by surgery, radiation or androgen deprivation therapy between 1-10 years prior to identification
- Has phone number on file and ability to converse on the telephone in English
- No dementia or other significant mental impairment

A random sample of those identified will be asked to participate. Those who elect to participate, and who have a qualifying Brief Screener score (1 or higher on at least 1 symptom) will be randomized to the study. We estimate as many as 553 - 650 veterans will be randomized. All participants will be 40-80 years old at the time of identification, and all will be male as this is a study of prostate cancer; otherwise we expect the health status of these veterans to be varied.

5.5 Study Evaluations

- **Describe all evaluations to be conducted (including screening; tests/questionnaires that will be administered; any procedures that subjects will be required to complete) and data collection methods. Include materials as an appendix or separate attachment.**

Potential participants will be sent an introductory packet from the AAVA. After one week, the coordinator will telephone those Veterans who did not opt-out, and if the patient is interested, the coordinator will administer the Brief Screener by phone and determine whether that Veteran meets the criteria of having a clinically meaningful symptom burden score (1 or higher on any one symptom, as a measure of low function or high symptom burden) on at least one item. Once the Veteran has been deemed eligible and the baseline survey has been administered, the veteran will be randomized to the automated telephone system or enhanced usual care (information about self-management).

Veterans randomized to the automated telephone system intervention will receive 4 automated phone calls over a 3-month period: 1 at study start and then once a month for 3 months. These calls will last approximately 15 minutes and will include questions about symptoms, will allow the veteran to identify a goal to work on, and help the veteran take steps towards reaching their goal and managing their symptoms. At the end of each call, the veteran will also have the option of listening to an audio testimonial tailored on priority symptom area. Following each call, the veteran will receive a personalized newsletter that will provide more details regarding their symptoms and strategies to help them manage their symptoms. Each newsletter will be 4 – 8 pages in length. The automated system will try to reach the veteran up to eight times over the course of 4 days (see IVR call schedule). If the veteran has not completed the call by day 3 of the call window, study staff will make up to 5 or 6 attempts to contact the patient (including leaving messages) to verify the phone number and preferred call time. If the veteran has still not completed the call by day 5 of the call window, study staff will again make up to 5 or 6 attempts to contact the patient. Following each reminder call, study staff have the option to initiate additional IVR calls should veteran be agreeable.

Veterans randomized to this group may also be contacted to participate in a 30 to 40-minute audio-recorded phone interview to find out about their experience with the program. These interviews will be conducted by the research staff at the Ann Arbor VA in Ann Arbor, MI. During the 12-month survey, veterans will be asked if they are interested in participating in the interview.

Veterans randomized to the control group will receive one 4-page newsletter with educational information about symptoms and symptom management, and will complete a survey over the phone at enrollment and at 5 and 12 months after starting the study.

Telephone surveys of both intervention and control groups to obtain baseline and follow-up measures will be conducted at three time points: baseline, five months, and 12 months post-enrollment. Hard copies of follow-up surveys will be sent to any participants expressing preference for completing the survey by paper and participants we are unable to reach by phone. Survey content will be finalized by our study team using established approaches during year 1 and pilot tested among prostate cancer survivors affiliated with the VAAHS prior to use in the trial. Each survey will be administered by the VA coordinator over the telephone. After each of these three assessments, both intervention and control group patients will be called by the IVR system for standardized administration of the EPIC. Baseline surveys will be done prior to randomization. Beginning approximately 4 months following enrollment, initial attempts will be made by the coordinating team to contact the participant by phone to complete the Time 2 survey, and approximately 11 months following enrollment to complete the Time 3 survey. For all 3 surveys, up to 5 or 6 attempts will be made to complete the survey, including leaving voice mails and providing call-back information for participants who are not home. Times to complete the surveys will be scheduled as desired by participants. Finally, if participants are unable or unwilling to complete the survey by telephone, a paper-and-pencil survey will be mailed to them with a return envelope. Participants who fail to return the paper survey within one month may be sent a second paper survey by mail. In addition, a reminder newsletter will be sent to participants 1-2 months prior to their expected 12-month follow-up. All participants completing the 12-month assessment will be sent an "early results" newsletter showing some preliminary survey results and thanking participants for their contribution to the study.

Patients are free to skip any survey questions administered by study staff that they would prefer not to answer. However, because the newsletters are tailored based on responses to questions administered by the automated telephone system, these questions are not optional. Nevertheless, patients are free to hang up the phone if they prefer not to complete an IVR call. Patients will also have the option to call into the IVR system using a toll free number if they prefer not to wait to complete their call.

We will use the Expanded Prostate Cancer Index (EPIC) to assess PC-symptom burden and associated PC-QOL at the baseline, 5- and 12-month assessments. The EPIC was developed by our study consultant, [name], and has been widely used in prostate cancer survivorship research. The EPIC is a 26-item measure that assesses symptom burden in four domains: urinary symptoms (9 items), bowel symptoms (6 items), sexual symptoms (6 items) and vitality (5 items). Each domain has a subscale related to function and bother which together contribute to disease specific quality of life. Prior work by [name] and colleagues has shown that these domains have good internal consistency (Chronbach's alpha > 0.82 for each domain) and correlate highly with other established measures of QOL.¹⁰⁷ Each domain has a range of possible scores from 0 to 100, with lower scores indicating worse symptom burden. Lower EPIC scores for any one domain are associated with lower function in that domain (e.g., lower sexual health function) and lower QOL. Thus higher symptom burden, which reflects both function and bother scores, translate into lower EPIC scores. Based on consultation with [name] and on prior work by his team, for purposes of this study we will consider a score of 70 or less to indicate "clinically meaningful symptom burden" for any one domain. We will conduct primary outcome analyses using the EPIC. Self-efficacy in patient-physician interactions will also be assessed both at baseline and 12-months using a 5-item short form version of the Perceived Efficacy in Patient-Physician Interactions (PEPPI). The PEPPI was developed to measure older patients' self-efficacy in obtaining medical information and attention to their medical concerns from physicians. PEPPI has good convergent and discriminant validity and strong reliability ($\alpha=0.93$).

At the 12-month assessment we will evaluate two key psychosocial domains of QOL (subjective health and perceptions of cancer control) that have been shown to be impacted by PC treatment in prior research. We will assess subjective health using the VR-12, an established measure of overall QOL that includes perceptions of one's health. We will assess perceived cancer control using a measure developed in prior research examining the psychosocial impact of prostate cancer; this measure includes three domains related to confidence that one's cancer is under control, worries about recurrence, and appraisals of one's coping with prostate cancer. We will evaluate these

outcomes at the 12-month assessment because that is when we expect the intervention would have its largest impact on these psychosocial domains of QOL.

The primary outcome for Specific Aim 2 will be use of VA services related to prostate cancer survivorship care at the 12 month assessment point. We will use the 12 month assessment point to ensure we capture any medication or service use related to prostate cancer symptom management that may occur after patients' exposure to the intervention has ended. Because there are no VA guidelines for appropriate management of prostate cancer survivors, we also will operationalize symptom-specific utilization consistent with MCC guidelines which are expert and evidence based. In the absence of VA guidelines for prostate cancer survivorship care, we considered national, regional and specialty organization guidelines. While there exists considerable overlap in recommendations, we ultimately chose the Michigan Cancer Consortium (MCC) guidelines for prostate cancer survivorship care as a standard against which to assess self-management approaches as well as use of services. We chose the MCC guidelines because they have good coverage of symptom management, the consortium is based in the same geographic area as our study sites, and because 2 study co-investigators contributed to their content ([name], [name]). We will operationalize utilization consistent with these guidelines using criteria mapping. This process has been used extensively to develop sets of quality metrics using a set of recommendations, when evidence-based guidelines do not exist, as is the case with prostate cancer survivorship care. Specifically, for each symptom indicated by the participant at baseline, we will determine potentially appropriate use of services by mapping receipt of services at the 12 month assessment to those outlined in the MCC recommendations. For analysis purposes, we will consider care recommended by the MCC as "guideline-concordant" even though the MCC are not fully evidence based guidelines. Data will be derived from three sources described in the Analytic Plan section below. For instance, if the patient indicates a problem with sexual function at baseline, we will measure use of pharmacologic treatments such as the phosphodiesterase inhibitors (sildenafil, tadalafil, vardenafil) or prostaglandin E1 (alprostadil as injection or intraurethral pellet), use of medical devices such as a vacuum erection device, a visit to a urologist, or receipt of surgery such as a penile prosthesis. Pharmacological agents for managing problems with urination include oxybutynin (Ditropan), tolterodine (Detrol) and phenazopyridine. Global measures for each symptom will indicate use of any of the pharmacologic, device, or referral measures suggested in the guideline. We also will create continuous measures of guideline-concordance service use from zero (none of the non-self-management approaches used in the prior year) to the maximum number of options for that specific symptom. Switching from one pharmacologic approach to another will be counted as separate approaches. The outcomes for Aim 2 (use of prostate cancer survivorship services consistent with those recommended by the MCC) will be obtained from two sources. We will collect pharmacy data, patient demographics, diagnoses, the date and type of utilization events, location of services (study site as well as clinic type), and the patients' assigned primary care provider from the Corporate Data Warehouse (CDW). To obtain information about device utilization, such as a penile clamp for incontinence control, we will use both CDW and the National Patient Prosthetics Database (NPPD) from Patient Care Services. Having the CDW and the NPPD records will ensure we can collect the most accurate device utilization. The process for requesting a data extract from these sources will be initiated at the end of year 2, to ensure sufficient time to obtain appropriate approvals for these datasets to be accessed by the data analyst from the AAVAHS.

We will collect information about participants' use of primary and specialty care from VA records in the 12 months between study enrollment and the final assessment. To account for services potentially received outside of the VA, we will ask participants at both the 5- and 12-month assessments to report the number of times over the prior interval that they visited their VA primary care physician and a specialist (urologist, oncologist, radiation oncologist, or gastroenterologist). For each visit, we will ask them to indicate whether the visit was related to their prostate cancer symptom management. We will also use the datasets created through Aim 2 to assess patients' use of primary and/or specialty care 12-months post enrollment.

